### 5.6.2 Adverse Events

The AE verbatim descriptions (investigator terms from the CRF) will be classified into standardized medical terminology using the Medical Dictionary for Regulatory Activities (MedDRA). Adverse events will be coded to the MedDRA (Version 21.1 or higher) lower level term (LLT) closest to the verbatim term. The linked MedDRA preferred term (PT) and primary system organ class (SOC) will also be captured in the database. The Common Terminology Criteria for Adverse Events (CTCAE) version 4.03 will be used to assess the severity of AEs.

A treatment-emergent adverse event (TEAE) is defined as an AE that emerged during treatment (up to 30 days after the subject's last dose of study drug), having been absent at pretreatment (Baseline) or

- Reemerged during treatment or up to 30 days following last dose of study drug, having been present at pretreatment (Baseline) but stopped before treatment, or
- Worsened in severity during treatment or up to 30 days following last dose of study drug relative to the pretreatment state, when the AE was continuous.

The serious AE that emerged up to 120 days after the subject's last dose of study drug is also counted as TEAE.

Only those AEs that are treatment emergent will be included in summary tables. All AEs, treatment emergent or otherwise, will be presented in subject data listings.

An overview table, including the incidence of and the number of subjects with TEAEs, TEAEs with grade 3 or above, serious adverse events (SAEs), deaths, and TEAEs that led to treatment discontinuation (discontinuation of both agents in arm A or B), dose reduction, or dose interruption will be provided by treatment arms.

The TEAEs will be summarized by treatment groups. The incidence of TEAEs will be reported as the number (percentage) of subjects with TEAEs by SOC and PT. A subject will be counted only once within a SOC and PT, even if the subject experienced more than 1 TEAE within a specific SOC and PT. The number (percentage) of subjects with TEAEs will also be summarized by maximum severity.

The number (percentage) of subjects with TEAEs will also be summarized by relationship to study drug. Summaries of TEAE incidence rate adjusted by treatment duration will be presented.

In summary, the following TEAE tables will be provided:

- Overview of TEAE and treatment-related TEAE
- TEAE by SOC and PT (Any Grade and Grade  $\geq 3$ , maximum grade 3, 4 and 5)
- TEAE by decreasing frequency of PT
- TEAE with each PT frequency  $\geq 5\%$  by PT
- TEAE by SOC, PT and Worst Grade of Toxicity
- Treatment-related TEAE by SOC and PT (Any Grade and Grade  $\geq 3$ )
- Exposure-adjusted TEAEs

The following subject AE listings (treatment emergent or otherwise) will be provided:

- All AEs
- All AEs with CTCAE Grade 3 or above

The proportion of subjects who discontinue treatment due to toxicity will be summarized by frequency counts and percentages. Median, upper and lower quartiles of time to treatment failure (discontinuation of both agents in arm A or B) due to toxicity will be summarized for subjects who discontinue study treatment due to TEAEs.

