- bb: All AEs will be captured up to 30 days after last dose of study drug. SAEs must be collected through 120 days after the subject's last dose, or 30 days following the last dose if the subject initiates new anticancer therapy, whichever is earlier. Any pregnancy in which the estimated date of conception is either before the last visit or within 120 days of the last study treatment or 30 days following last study treatment if the subject initiates new anticancer therapy, whichever is earlier, must be reported. Also, any exposure to study drug through breastfeeding during study treatment or within 120 days of the last study treatment, or 30 days following the last study treatment if the subject initiates a new anticancer therapy, whichever is earlier, must be reported.

Table 8 Schedule of Visits and Procedures in E7080-G000-307 Extension Phase

Phase	Extension			
	Treatment Period			Follow-Up Period
Period				
Visit	100-998	101-997	999 ^p	1000
	Cycle X (Last Cycle +1) and Beyond ^a		Off-Treatment Visit	
Day	1	15		
Assessments				
KPS ^b	X		X	
Vital signs and weight ^c	X	X ^c	X	
Physical Examination ^c	X		X	
12-lead ECG ^f	X		X	
MUGA scan or echocardiogram ^g			X	
Hematology and clinical chemistry ^h	X		X	
Urine dipstick testing ^d	X	X ^d	X	
Pregnancy test ⁱ	X		X	X
Biomarker (serum) sample ^j			X	
Biomarker (plasma) sample ^j			X	
Biomarker (whole blood) sample ^j			X	
Tumor assessments: CT (MRI) ^k	Tumor assessments will be performed according to the local standard of care.			
Bone Scan	Bone scans will be performed if clinically indicated.			
Brain Scan	Brain scans will be performed if clinically indicated.			
Survival and PFS ^l				X
Study drug treatment	21-day cycles of lenvatinib daily plus everolimus daily or 21-day cycle of lenvatinib daily plus pembrolizumab IV every 21 days or sunitinib daily for 4 weeks plus 2 weeks off, depending on randomization arm			
Concomitant medications ^m	Throughout			X
AEs/SAEs ^{n,o}	Throughout			X

Table 8 Schedule of Visits and Procedures in E7080-G000-307 Extension Phase

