9.5.4.1 Reporting of Serious Adverse Events

All SERIOUS ADVERSE EVENTS, regardless of their relationship to study treatment, must be reported on a completed SAE form by email or fax as soon as possible but no later than 24 hours from when the investigator becomes aware of the event.

SAEs regardless of causality assessment must be collected through the last visit and for 120 days after the subject's last dose, or 30 days following the last dose if the subject initiates new anticancer therapy, whichever is earlier.

Regardless of treatment arm, all SAEs must be followed to resolution or, if resolution is unlikely, to stabilization. Any SAE judged by the investigator to be related to the study treatment or any protocol-required procedure should be reported to the sponsor regardless of the length of time that has passed since study completion.

The detailed contact information for reporting of SAEs is provided in the Investigator Study File.

For urgent safety issues, please ensure all appropriate medical care is administered to the subject and contact the appropriate study team member listed in the Investigator Study File.

It is very important that the SAE report form be filled out as completely as possible at the time of the initial report. This includes the investigator's assessment of causality.

Any follow-up information received on SAEs should be forwarded within 24 hours of its receipt. If the follow-up information changes the investigator's assessment of causality, this should also be noted on the follow-up SAE form.

Preliminary SAE reports should be followed as soon as possible by detailed descriptions including copies of hospital case reports, autopsy reports, and other documents requested by the sponsor.

For sites in the US, the investigator must notify his/her IRB/IEC of the occurrence of the SAE in writing, if required by their institution. A copy of this communication must be forwarded to the sponsor and/or the designated CRO, depending on responsibility for regulatory documents, to be filed in the sponsor's Trial Master File.

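### SAP 5.6.2 counts serious adverse events to day 120 in every subject, but the protocol collects them systematically only to day 30 in subjects who start new anticancer therapy

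*SAP*

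**What the plan says.** SAP 5.6.2 works with two windows. An adverse event of any kind is treatment-emergent if it appears, recurs or worsens up to 30 days after the last dose. For serious events a further sentence applies: "The serious AE that emerged up to 120 days after the subject's last dose of study drug is also counted as TEAE". New anticancer therapy is not mentioned. The main summary is a crude proportion: "The incidence of TEAEs will be reported as the number (percentage) of subjects with TEAEs by SOC and PT". SAP 5.6.2.1 adds tables by treatment group for SAEs, treatment-related SAEs, fatal TEAEs and exposure-adjusted SAEs.

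Protocol 9.5.4.1 has SAEs collected, whatever their causality, for "120 days after the subject's last dose, or 30 days following the last dose if the subject initiates new anticancer therapy, whichever is earlier". The same rule appears in the Synopsis, Sections 9.1.2.1, 9.1.3.1 and 9.5.1.4.1, Table 7 (footnote bb) and Table 8 (footnote n). Section 9.5.4.1 leaves one route open afterwards: an SAE that the investigator judges related to study treatment or to a protocol procedure "should be reported to the sponsor regardless of the length of time that has passed since study completion".

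Two other SAP passages bear on the point. Section 5.3.6 ends the safety summaries at end of treatment plus an applicable window that it does not define. Section 5.6.1.1 defines treatment duration as running from first to last dose.

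**The concern.** The SAP's counting window is longer than the protocol's collection window for one group of subjects: those who start new anticancer therapy within 120 days of their last dose. In that group the later SAEs on file are a selected remainder. They comprise events judged related, events reported before the new therapy began, and whatever events on next-line treatment a site happens to report. The SAP labels all of them treatment-emergent for study drug. Subjects without new therapy are collected in full to day 120.

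At stake is how the SAE tables, the fatal-TEAE table and the TEAE overview are read. Death is a seriousness criterion (Protocol 9.5.1.4.2), so fatal events inherit the 120-day rule. Comparing safety with sunitinib is a stated secondary objective (SAP 3.1.2). A crude percentage presented as if every subject had 120 days of follow-up will mislead if the arms differ in how many subjects leave collection at day 30.

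**Working it through.** The plan states no figure to reproduce. The first check sets the texts side by side; the second is an illustration on assumed rates.

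**1. Windows, in days after the last dose**

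| Subject | Counted (SAP 5.6.2) | Collected, any causality (Protocol 9.5.4.1) | Counted but not systematically collected |
|---|---|---|---|
| No new therapy by day 120 | 120 | 120 | 0 |
| New therapy by day 30 | 120 | 30 | 120 − 30 = 90 (75%) |
| New therapy on day 60 | 120 | 30 if the rule is read literally; 60 if sites collect until therapy starts | 90 (75%) or 60 (50%) |
| New therapy on day 90 | 120 | 30 or 90 | 90 (75%) or 30 (25%) |

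So 75% is a maximum per affected subject. The table also shows an ambiguity. Read literally, the protocol cuts back to day 30 even when therapy starts later. An SAE on day 45 before a day-60 start would then be counted by the SAP but lie outside the protocol window.

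**2. Does anything in the SAP correct this?** The exposure-adjusted tables divide by treatment duration, which stops at the last dose (SAP 5.6.1.1), so 30 versus 120 days of follow-up does not enter the denominator. Section 5.3.6 does not define its window. No SAP text ends SAE counting at new therapy.

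**3. When are the arms distorted?** Let f be the share of an arm's stopped subjects who start new therapy within 120 days. Under the literal rule the mean collection window is 120 − 90f days: 102 at f = 0.2, 84 at f = 0.4, 66 at f = 0.6.

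Let p30 and p120 be the probabilities of a first SAE by day 30 and by day 120, equal in both arms. The expected recorded proportion is (1 − f)·p120 + f·p30, so the spurious difference between two arms is Δf × (p120 − p30). It is zero when Δf = 0.

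With an assumed constant monthly hazard h, p(t) = 1 − exp(−h·t/30.4375):

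| h per month (assumed) | p30 | p120 | p120 − p30 | f = 0.3 vs 0.5 | f = 0.2 vs 0.6 |
|---|---|---|---|---|---|
| 0.02 | 0.0195 | 0.0758 | 0.0563 | 1.1 points | 2.3 points |
| 0.05 | 0.0481 | 0.1789 | 0.1308 | 2.6 points | 5.2 points |
| 0.10 | 0.0939 | 0.3258 | 0.2320 | 4.6 points | 9.3 points |

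Milder assumptions give less. With Δf = 0.10 and a 5% chance of a first SAE in days 31–120, the result is 0.10 × 0.05 = 0.5 points. With 0.30 and 10% it is 3 points.

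All these figures treat every SAE after day 30 in starters as lost and refer only to subjects who have stopped treatment. Related SAEs remain reportable, and the tables use the whole Safety Analysis Set, including subjects still on treatment. Both make the effect in the tables smaller.

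**The case against.** The strongest reply is that the SAP creates no inequality. The protocol's collection rule does, and rewriting the SAP to match it leaves the windows unequal. That is correct; what the SAP adds is the appearance of a uniform 120 days.

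Several facts limit the consequence. The safety analyses are descriptive. Non-serious events already share a 30-day window. All SAEs are listed whether treatment-emergent or not (SAP 5.6.2.1), and anticancer therapy is recorded until death or the end of survival follow-up (Table 7, footnote aa). A truncation could also sit in the separate programming specifications (SAP 9), but nothing in the SAP says so, and its own sentence says otherwise.

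The long window is also deliberate. The revision history says SAE collection was lengthened at the request of regulatory authorities, and Protocol 9.4.3 notes that immune-related events may occur several months after the last dose. This stands, and it argues against replacing the main tables with 30-day ones.

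A reader might infer more than the documents support:

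- That SAE collection ceases at day 30. It does not, since related SAEs stay reportable without limit. For the same reason the treatment-related SAE table is the least exposed, although late capture then rests on causality judgements in an open-label trial.
- That SAE incidence is understated on sunitinib. The design assumes median PFS of 12.3 months on sunitinib against 17.2 months on the combinations, and the option to stop in confirmed complete response is framed around pembrolizumab. This makes different uptake plausible, but neither fact gives the share starting new therapy within 120 days of the last dose. Missed unrelated SAEs lower an arm's count, while next-line SAEs that are reported raise it, so the net direction is unknown.

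**Conclusion.** The mismatch is literal and nothing in the SAP repairs it. Followed as written, the SAP counts SAEs over days that the protocol does not systematically collect in subjects who start new therapy within 120 days, and it attributes reported next-line SAEs to study drug.

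The size per affected subject is at most 90 of 120 days. A distortion between arms needs a further condition, different uptake of new therapy by arm, on which the documents are silent. The 0.5 to 9.3 points in the illustration depend entirely on assumed shares and SAE rates and should not be quoted as an estimate.

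Type I error and the primary endpoint are untouched. The effect is on the interpretation of the crude SAE, fatal-TEAE and overview tables. It is worth correcting because the rule is wrong as written and the data needed are already recorded.

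**What to change.** In SAP 5.6.2:

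1. Align the serious-TEAE rule with the protocol's collection window. Apply the new-therapy exception only when that therapy starts within 120 days of the last dose; without that limit, a start on day 200 would wrongly cut counting to day 30 after full collection to day 120.
2. State how SAEs with onset after day 30 but before new therapy are handled, so that validly collected events are not discarded.
3. Keep the main SAE tables on the aligned window. Add supplementary between-arm SAE and fatal-TEAE tables on the 30-day window, which is collected in every subject.
4. Add a table of SAEs from days 31–120 with the number of subjects still under collection in each arm.

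Step 1 alone removes the contradiction but not the inequality. Under the illustration's equal hazards, the common 30-day tables contain no window artefact. The cost is SAP wording and a small number of extra tables, with no new data. The downside is that a few late SAEs on next-line therapy move from the summary tables to the listings. Late immune-related SAEs within the aligned window stay in the main tables.

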9.1.2.1 Treatment Period

The Treatment Period for each subject will begin at the time of randomization and will end with the completion of the Off-Treatment Visit, which will occur within 30 days after the final dose of study treatment. All AEs will be captured up to 30 days after last dose of study drug. Serious AEs must be collected for 120 days after the subject's last dose of study drug, or 30 days following the last dose of study drug if the subject initiates new anticancer therapy, whichever is earlier.

- Subjects will receive study treatment as continuous 21-day cycles. Treatment cycles will be counted continuously regardless of dose interruptions. Subjects will undergo safety and efficacy assessments as defined in the Schedule of Procedures/Assessments. Subjects will continue to receive study treatment until confirmed PD by IIR, development of unacceptable toxicity, subject request, withdrawal of consent, completion of 35 treatments (approximately 2 years) with pembrolizumab, or study termination by the sponsor.
- Subjects in Arm B who discontinue pembrolizumab after 35 treatments may continue treatment with lenvatinib alone unless any other criteria above apply.
- Discontinuation of treatment may be considered for those subjects who fulfill all of the following criteria: attain a confirmed CR, have been treated for at least 8 cycles (at least 24 weeks) with pembrolizumab, and have received at least 2 treatments with pembrolizumab beyond the date when the initial CR is declared. In the presence of clinical benefit, subjects who complete treatment with pembrolizumab may continue to receive lenvatinib alone after this time point.

Subjects will be permitted to continue study treatment beyond RECIST 1.1-defined disease progression as long as the treating investigator considers that there is clinical benefit, and the subject is tolerating study drug. The assessment of clinical benefit should take into account whether the subject is clinically deteriorating and unlikely to receive further benefit from continued treatment. All decisions to continue treatment beyond initial progression must be discussed with the Eisai Medical Monitor. Subjects will discontinue study treatment upon evidence of further progression and/or loss of clinical benefit as judged by the Investigator.

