### 5.6.1 Extent of Exposure

#### 5.6.1.1 Study Treatment Extent of Exposure

Duration of treatment for study medications individually and/or in combination (overall) will be summarized with descriptive statistics. The dosing end date will be imputed to the analysis cutoff date if the subject is still on treatment at the time of the data cutoff, and the dose will be imputed with the last dose recorded in the database for that subject.

The duration of individual study drug in months will be  $(\text{Date of the last dose} - \text{Date of the first dose} + 1) / 30.4375$ , including drug interruption days. For overall treatment duration, it is defined as the duration between the earliest first dose start date of study drugs and the latest last dose end date of study drugs.

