### 5.6.2.1 Deaths, Serious and Other Significant Adverse Events

The number (percentage) of subjects with TEAEs leading to death will be summarized by MedDRA SOC and PT for each treatment group. A subject data listing of all AEs leading to death will be provided.

The number (percentage) of subjects with treatment-emergent serious adverse events (SAEs) was summarized by MedDRA SOC and PT for each treatment group. A subject data listing of all SAEs was provided.

The number (percentage) of subjects with TEAEs leading to discontinuation from study drug will be summarized by MedDRA SOC and PT for each treatment group. A subject data listing of all AEs leading to discontinuation from study drug will be provided. The number (percentage) of subjects with TEAE leading to study drug dose reduction or interruption will also be summarized by MedDRA SOC and PT for each treatment group. A subject data listing of all AEs leading to study drug dose reduction or interruption will be provided.

In summary, the following TEAE tables will be provided:

- TEAE leading to death by SOC and PT
- SAEs by SOC and PT
- Treatment-related SAEs by SOC and PT
- SAEs by decreasing frequency of PT
- Nonfatal SAEs by decreasing frequency of PT
- Exposure-adjusted SAEs
- TEAE leading to drug discontinuation by SOC and PT
- TEAE leading to drug discontinuation of Lenvatinib by SOC and PT
- TEAE leading to drug discontinuation of Everolimus/Pembrolizumab by SOC and PT
- TEAE leading to drug reduction and/or interruptions by SOC and PT
- TEAE leading to drug reduction and/or interruptions of Lenvatinib by SOC and PT
- TEAE leading to drug reduction and/or interruptions Everolimus/Pembrolizumab by SOC and PT

The following subject AE listings (treatment-emergent or otherwise) will be provided:

- All AEs with fatal outcome
- All SAEs
- All AE leading to study drug discontinuation
- All AEs leading to study drug dose reduction and/or interruption

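### Exposure-adjusted TEAE rates count events after the last dose but divide by time to the last dose only; the adjusted SAE table states no denominator and appears to do the same

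*SAP*

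**What the plan says.** **Numerator.** SAP 5.6.2 treats an adverse event as treatment-emergent if it arises up to 30 days after the last dose. It adds a longer rule for serious events: "The serious AE that emerged up to 120 days after the subject's last dose of study drug is also counted as TEAE".

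**Denominator.** The same section says "Summaries of TEAE incidence rate adjusted by treatment duration will be presented". SAP 5.6.1.1 defines overall treatment duration as "the duration between the earliest first dose start date of study drugs and the latest last dose end date of study drugs", with no post-dose period added. For anyone still taking study drug when the data are cut, it sets the end of dosing to the cutoff, so such a subject has no post-dose window.

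**Tables.** SAP 5.6.2 lists an exposure-adjusted TEAE table, and SAP 5.6.2.1 lists "Exposure-adjusted SAEs". Neither carries a formula. SAP 5.3.6 extends what is summarized by a window for each endpoint but does not extend exposure time.

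**Collection.** Protocol 9.1.2.1 collects SAEs for 120 days after the last dose, or for "30 days following the last dose of study drug if the subject initiates new anticancer therapy, whichever is earlier". The SAP's 120-day rule does not mention this shorter limit.

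**The concern.** Events are drawn from treatment time plus a tail, while the divisor is treatment time alone. A tail of fixed length is a larger fraction of a short treatment period than of a long one, so the error depends on treatment duration. That is the quantity exposure adjustment is meant to neutralise.

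Comparing safety and tolerability of each combination with sunitinib is a secondary objective (SAP 3.1.2). If one arm is treated for less time, its adjusted rates would look somewhat too high against the other, most visibly for SAEs, where the tail is four months. The tail also differs between subjects, because starting new therapy shortens SAE collection.

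**Working it through.** The documents state no exposure-adjusted rate, so there is no figure to reproduce. The check measures how far the rule as written moves a rate ratio that is truly 1.00.

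**Inputs**
- Windows *w*: 30 and 120 days (SAP 5.6.2). At 30.4375 days per month (SAP 8.2.2), these are 0.986 and 3.943 months.
- Treatment duration *T*: the documents give about 15 months for all subjects (Protocol Synopsis, Duration of Treatment) and nothing by arm. As an assumption, I use the design median PFS of 12.3 months (Arm C) and 17.2 months (Arms A and B) from SAP 4.
- Enrollment over 34 months, with PFS analyses at 38 and 45 months (SAP 4).

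**Formula.** Let *f* be the share of subjects off treatment with a full window, and *h* the post-treatment event rate relative to the on-treatment rate. The stated rate exceeds the matched rate by the factor 1 + *f·h·w/T*.

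**Upper bound (*f* = *h* = 1)**
- *T* = 15 months: 1 + 0.986/15 = 1.066 and 1 + 3.943/15 = 1.263.
- *T* = 12.3 months: 1.080 and 1.321.
- *T* = 17.2 months: 1.057 and 1.229.
- Apparent ratio, longer against shorter arm: 1.057/1.080 = 0.979 (30 days) and 1.229/1.321 = 0.931 (120 days).

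**Staggered entry and cutoff.** I simulated uniform entry over 34 months and exponential treatment durations with medians of 12.3 and 17.2 months. Post-dose windows were truncated at cutoff; deaths within the window were not modelled. At 38 months the shares off treatment are 0.645 and 0.536, and the mean treatment times 11.4 and 13.3 months. As a rough check for 120 days in the shorter arm, 0.645 × 3.943/11.44 = 0.222. The simulation gives 0.208, because cutoff shortens some windows.

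| Scenario | 30 days: 12.3 / 17.2 | Ratio | 120 days: 12.3 / 17.2 | Ratio |
|---|---|---|---|---|
| All off treatment, full window | 1.080 / 1.057 | 0.979 | 1.321 / 1.229 | 0.931 |
| Staggered entry, cutoff 38 months | 1.055 / 1.039 | 0.985 | 1.208 / 1.147 | 0.950 |
| Staggered entry, cutoff 45 months | 1.055 / 1.039 | 0.985 | 1.213 / 1.152 | 0.949 |
| Cutoff 38, half cut to 30 days by new therapy | – | – | 1.131 / 1.093 | 0.966 |
| Cutoff 38, all cut to 30 days | – | – | 1.055 / 1.039 | 0.985 |
| Full window, post-treatment rate one quarter | 1.020 / 1.014 | 0.994 | 1.080 / 1.057 | 0.979 |

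The 30-day columns apply to events counted to 30 days. The TEAE table as defined also takes in serious events from days 31 to 120, so its overall distortion lies between the two sets of columns.

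**Direction.** Inflation is equal in the two arms when *h/T* is equal, that is, when the longer-treated arm has a post-treatment rate 17.2/12.3 = 1.40 times that of the shorter-treated arm. Above that the bias reverses.

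**After correction.** With a matched denominator, or with on-treatment events over treatment duration, the factor is 1.00 in every arm under a constant event rate.

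**The case against.** The SAP gives no formula for either table. Programming specifications and table shells sit in separate documents (SAP 9 and 11) and could already define a matched time at risk. That stands as a reason for caution, most of all for SAEs: a reader might infer that the SAP prescribes treatment duration as the SAE denominator, but only a table title is given. For TEAEs the sentence in 5.6.2 does name treatment duration, so the mismatch there is in the stated rule and is more than missing detail.

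A reader might also infer that the bias favours the combinations. The documents do not establish this. No treatment duration is given by arm, and the direction needs similar post-treatment event rates. Protocol 9.4.3 warns that immune-related events can appear several months after the last pembrolizumab dose, which could offset or reverse the effect in Arm B.

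Larger distortions can be produced by assuming a wider gap. At 8 against 17 months the SAE factors are 1.493 and 1.232, a ratio of 1.21 for the shorter arm, but nothing in the documents supports those exposures. The rule that cuts SAE collection to 30 days makes the tail uneven between subjects, yet it reduces the average bias.

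Finally, crude incidences, deaths, discontinuations and listings are all reported without this denominator, and no test or decision rule uses the adjusted rates. That limits the consequence but leaves the two tables miscalculated as described.

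**Conclusion.** The concern holds in a limited form. The stated TEAE rule has a numerator window longer than its denominator; for SAEs the same denominator is inferred. If post-treatment event rates are similar across arms, the shorter-treated arm is inflated more.

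With design median PFS as an assumed proxy for treatment duration, a true ratio of 1.00 would appear as 0.93 for SAEs at the extreme, and more plausibly between 0.95 and 0.985 depending on cutoff and new therapy. The effect on events counted to 30 days is 2% or less after rounding. Both would be smaller if event rates drop after treatment stops. The direction is conditional, and the figures are illustrations rather than forecasts. Since the tables are descriptive, the case for changing them is that the correction is cheap and removes a bias that depends on treatment duration.

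**What to change.** State the denominator in SAP 5.6.2 and 5.6.2.1, choosing one of two forms.

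- **(a) On-treatment events only.** For the exposure-adjusted tables, count events with onset from first to last dose and divide by treatment duration as defined in 5.6.1.1.
- **(b) Matched person-time.** Run person-time for non-serious TEAEs to last dose + 30 days. For serious AEs, run it to last dose + 120 days, or + 30 days if new anticancer therapy starts. Truncate each at death and data cutoff. In the overall exposure-adjusted TEAE table, use a single 30-day window for all events and show serious AEs from days 31 to 120 only in the SAE table. Otherwise those events would stay in the numerator outside a 30-day denominator.

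A flat 120 days for everyone would over-correct where collection stopped at 30.

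**Cost.** SAP wording and a derived time-at-risk variable, from dosing, death, new-therapy and cutoff dates the plan already needs. Adjusted rates fall in all arms. Under (b), SAE rates fall by up to 1 − 1/1.321 = 24% at 12.3 months and 1 − 1/1.229 = 19% at 17.2 months. Option (a) drops post-dose events, but from these tables only; they remain in the crude tables and listings.
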